#### **RECOMMENDATIONS:**

1. If you forget to apply a dose, do not double the dose to “catch up”. If your next dose is scheduled within the next 12 hours, it is best just to wait; if it is more than 12 hours until your next dose, apply the dose you missed and resume your normal dosing after that.
2. For the duration of the study, avoid contact between the application area and the skin of other individuals (i.e. your child, your sexual partner, or other persons). If necessary, skin contact is allowable after the breasts have been washed. As noted above, you must wait at least 4 hours following application before washing the application area, otherwise, delay application until after washing and contact.

3. Do not ingest or swallow the gel. For external use only.
4. Please record your use of 4-OHT in your 4-OHT diary.
5. If the pump doesn't come back up correctly or if there's no gel delivered when you press down on the pump, do not use this bottle and notify your doctor immediately.
6. After the end of study treatment, be sure to take back to your doctor **all** the gel bottles you have been given (even if empty or not used). **This is very important for the success of the study.**

## **STORAGE INSTRUCTIONS:**

1. Keep your gel bottles in a cool room temperature, between 59°F and 77°F.
2. Avoid extreme heat or cold during transportation from the clinic to home, and when traveling.
3. Keep the gel bottles out of the reach of children.

## **TRAVEL:**

Your gel is a prescription medication. You may bring the gel in your carry-on bag. Please refer to the Transportation Security Administration web site for further details: <https://www.tsa.gov/travel/special-procedures>

**APPENDIX C**

**COMPLIANCE DRUG LABELS**

*(Use this Form at Randomization and Month 6)*

INSTITUTION CODE _____	PARTICIPANT ID _____	VISIT TYPE _____	VISIT DATE (MM/DD/YYYY) ___/___/_____
---------------------------	-------------------------	---------------------	---

**Affix Labels Here:**

Were Labels Affixed?

Yes

No

Investigator's Signature: \_\_\_\_\_

Date of Investigator's Signature: \_\_/\_\_/\_\_\_\_\_  
(MM/DD/YYYY)

Investigator's Name (Please Print): \_\_\_\_\_

## **APPENDIX D**

### **4-OHT Diary**

**4-OHT Diary [IRB #: \_\_\_\_\_ ]**

PID: \_\_\_\_\_ Site: \_\_\_\_\_

Amount of Agent Provided: \_\_\_\_\_ canisters

Canister \_\_\_ of 5

Total Daily Dose: 1 pump actuation to each breast once a day [4 mg total (2 mg per breast)]

Number of Canisters Returned: \_\_\_\_\_

Weight of Canisters Returned: \_\_\_\_\_ (grams)

Agent Returned:  Yes  No

Visit#: \_\_\_\_\_

**INSTRUCTIONS:**

1. Please complete daily. You should apply 1 pump actuation to each breast once a day.
2. If you forget to apply a dose, do not double the dose to “catch up”. If your next dose is scheduled within the next 12 hours, it is best just to wait; if it is more than 12 hours until your next dose, apply the dose you missed and resume your normal dosing after that.
3. Each canister provides 40 days of gel application for both breasts. After 40 days of gel application, switch to a new canister and calendar. Do not discard any canisters. Bring all used and unused canisters and calendars to your next appointment.
4. Store the study gel at home at room temperature and avoid extreme heat or cold during transportation from the clinic to home.

### 4-OHT Diary Continued

*Please Bring this Sheet to Your Next Visit*

Day	Date	Initials	# of pump actuations to right breast	# of pump actuations to left breast	Did you experience any symptoms, if "Yes" list below
1			_____ or  Missed Dose	_____ or  Missed Dose	
2			_____ or  Missed Dose	_____ or  Missed Dose	
3			_____ or  Missed Dose	_____ or  Missed Dose	
4			_____ or  Missed Dose	_____ or  Missed Dose	
5			_____ or  Missed Dose	_____ or  Missed Dose	
6			_____ or  Missed Dose	_____ or  Missed Dose	
7			_____ or  Missed Dose	_____ or  Missed Dose	
8			_____ or  Missed Dose	_____ or  Missed Dose	
9			_____ or  Missed Dose	_____ or  Missed Dose	
10			_____ or  Missed Dose	_____ or  Missed Dose	
11			_____ or  Missed Dose	_____ or  Missed Dose	
12			_____ or  Missed Dose	_____ or  Missed Dose	
13			_____ or  Missed Dose	_____ or  Missed Dose	
14			_____ or  Missed Dose	_____ or  Missed Dose	
15			_____ or  Missed Dose	_____ or  Missed Dose	
16			_____ or  Missed Dose	_____ or  Missed Dose	
17			_____ or  Missed Dose	_____ or  Missed Dose	
18			_____ or  Missed Dose	_____ or  Missed Dose	
19			_____ or  Missed Dose	_____ or  Missed Dose	
20			_____ or  Missed Dose	_____ or  Missed Dose	

21			       or  Missed Dose	       or  Missed Dose	
22			       or  Missed Dose	       or  Missed Dose	
23			       or  Missed Dose	       or  Missed Dose	
24			       or  Missed Dose	       or  Missed Dose	
25			       or  Missed Dose	       or  Missed Dose	
26			       or  Missed Dose	       or  Missed Dose	
27			       or  Missed Dose	       or  Missed Dose	
28			       or  Missed Dose	       or  Missed Dose	
29			       or  Missed Dose	       or  Missed Dose	
30			       or  Missed Dose	       or  Missed Dose	
31			       or  Missed Dose	       or  Missed Dose	
32			       or  Missed Dose	       or  Missed Dose	
33			       or  Missed Dose	       or  Missed Dose	
34			       or  Missed Dose	       or  Missed Dose	
35			       or  Missed Dose	       or  Missed Dose	
36			       or  Missed Dose	       or  Missed Dose	
37			       or  Missed Dose	       or  Missed Dose	
38			       or  Missed Dose	       or  Missed Dose	
39			       or  Missed Dose	       or  Missed Dose	
40			       or  Missed Dose	       or  Missed Dose	

Participant Signature: \_\_\_\_\_ Date: \_\_\_\_\_

Reviewer's Signature: \_\_\_\_\_ Date: \_\_\_\_\_

Comments:

---

---

---

## **APPENDIX E**

### **BESS QUESTIONNAIRE**

*\*The completed form is to be used as source*

**BESS QUESTIONNAIRE**

INSTITUTION CODE  _____	PARTICIPANT ID  _____	VISIT TYPE  _____	VISIT DATE (MM/DD/YYYY)  ____/____/____
-------------------------------	-----------------------------	-------------------------	--

We are interested in knowing whether you have had any of the following problems during the **PAST TWO WEEKS**. Please mark the number which best describes how much each problem bothered you.

PROBLEM		Not at all	Slightly	Moderately	Quite a bit	Extremely
C1	Difficulty concentrating	0	1	2	3	4
C2	Easily distracted	0	1	2	3	4
C3	Forgetfulness	0	1	2	3	4
M1	Joint pain	0	1	2	3	4
M2	Muscle stiffness	0	1	2	3	4
M3	General aches and pains	0	1	2	3	4
V1	Night sweats	0	1	2	3	4
V2	Hot flashes	0	1	2	3	4
V3	Cold sweats	0	1	2	3	4
Ga1	Vomiting	0	1	2	3	4
Ga2	Nausea	0	1	2	3	4
Ga3	Diarrhea	0	1	2	3	4
D1	Vaginal dryness	0	1	2	3	4
D2	Pain with intercourse	0	1	2	3	4
W1	Weight gain	0	1	2	3	4
W2	Unhappy with the appearance of my body	0	1	2	3	4
Gy1	Vaginal discharge	0	1	2	3	4
Gy2	Genital itching/irritation	0	1	2	3	4
Gy3	Vaginal bleeding or spotting	0	1	2	3	4
B1	Difficulty with bladder control (when laughing or crying)	0	1	2	3	4

**BESS QUESTIONNAIRE (cont'd)**

INSTITUTION CODE  _____	PARTICIPANT ID  _____	VISIT TYPE  _____	VISIT DATE (MM/DD/YYYY)  ____/____/____
-------------------------------	-----------------------------	-------------------------	--

PROBLEM		Not at all	Slightly	Moderately	Quite a bit	Extremely
B2	Difficulty with bladder control (at other times)	0	1	2	3	4
P1	Headaches	0	1	2	3	4
P2	Blind spots, fuzzy vision	0	1	2	3	4
P3	Constipation	0	1	2	3	4
P4	Cramps	0	1	2	3	4
P5	Breast sensitivity/tenderness	0	1	2	3	4
P6	Ringing in ears	0	1	2	3	4
P7	Chest pains	0	1	2	3	4
P8	Swelling of hands or feet	0	1	2	3	4
P9	Difficulty breathing	0	1	2	3	4
P10	Dry mouth	0	1	2	3	4
P11	Weight loss	0	1	2	3	4
P12	Decreased appetite	0	1	2	3	4
P13	Feeling of suffocation	0	1	2	3	4
P14	Excitability	0	1	2	3	4
P15	Short temper	0	1	2	3	4
P16	Tendency to take naps; stay in bed	0	1	2	3	4
P17	Tendency toward accidents	0	1	2	3	4
P18	Avoidance of social affairs	0	1	2	3	4
P19	Dizziness, faintness	0	1	2	3	4
P20	Numbness, tingling	0	1	2	3	4

**BESS QUESTIONNAIRE (cont'd)**

INSTITUTION CODE  _____	PARTICIPANT ID  _____	VISIT TYPE  _____	VISIT DATE (MM/DD/YYYY)  ____/____/____
-------------------------------	-----------------------------	-------------------------	--

P21	Early awakening	0	1	2	3	4
P22	Abdominal pain	0	1	2	3	4
P23	Pain or cramps in the legs or feet	0	1	2	3	4
P24	Back pain or problems	0	1	2	3	4
P25	Low energy	0	1	2	3	4
P26	Blurred vision	0	1	2	3	4
P27	Any other problems?	Please Specify: _____ _____ _____				

\_\_\_\_\_  
Participant Name

\_\_\_\_\_  
Participant Signature

\_\_\_\_\_  
Date

**APPENDIX F**

**Alcohol and Tobacco Use Assessment Questionnaires – Baseline**

ALCOHOL ASSESSMENT – BASELINE

INSTITUTION CODE _____	PARTICIPANT ID _____	VISIT TYPE _____	VISIT DATE (MM/DD/YYYY) ____/____/____
---------------------------	-------------------------	---------------------	--

**Instructions:**

**For the following questions about drinking alcoholic beverages, a drink means a 12 oz. beer, a 5 oz. glass of wine, or one and a half ounces of liquor.**

1. In your entire life, have you had at least 12 drinks of any kind of alcoholic beverage?

- Yes
- No **(End)**
- Refused **(End)**
- Don't know/Not sure

2. In the past 12 months, on average, how often did you drink any type of alcoholic beverage?

\_\_\_\_\_ (Enter the number of days you drank based on the timeframe checked below. Enter 0 if you never drank and skip to Question 6.)

- Week
- Month
- Year
- Refused
- Don't know/Not sure

3. In the past 12 months, on those days that you drank alcoholic beverages, on average, how many drinks did you have per day?

\_\_\_\_\_ (Enter the average number of drinks per day)

- Refused
- Don't know/Not sure

4. In the past 12 months, on how many days did you have 5 or more drinks of any alcoholic beverage?

\_\_\_\_\_ (Enter the number of days you had 5 or more drinks, or enter 0 if none.)

- Refused
- Don't know/Not sure

5. Was there ever a time or times in your life when you drank 5 or more drinks of any kind of alcoholic beverage almost every day?

- Yes
- No
- Refused

# Proprietary of MD Anderson Cancer Center

MDA2016-07-02  
Protocol Version 20, Dated 02/07/2022

Don't know/Not sure

6. If you do not currently drink alcoholic beverages, but did in the past, how long has it been since you last drank regularly?

- Within the past month (0 to 1 month ago)
- Between 1 and 3 months (1 to 3 months ago)
- Between 3 and 6 months (3 to 6 months ago)
- Between 6 and 12 months (6 to 12 months ago)
- Between 1 and 5 years (1 to 5 years ago)
- Between 5 and 15 years (5 to 15 years ago)
- More than 15 years ago
- Don't know/Not sure
- Never drank regularly

7. At the heaviest point, either now or in the past, on the days when you drank, about how many drinks did you drink a day on the average?

\_\_\_\_\_ (Enter the number of drinks a day)

- Refused
- Don't know/Not sure

8. How many years have you been drinking (or did drink) regularly?

\_\_\_\_\_ years

- Refused
- Don't know/Not sure

9. At what age did you begin drinking regularly?

\_\_\_\_\_ years of age

- Refused
- Don't know/Not sure

10. What type(s) of alcohol do you drink? (Mark ALL that apply)

- Wine
- Liquor
- Beer
- Wine cooler

Signature of Individual Completing This Form \_\_\_\_\_ Date    /   /     
(MM/DD/YYYY)

Name of Individual Completing This Form (please print) \_\_\_\_\_

**TOBACCO ASSESSMENT – BASELINE**

INSTITUTION CODE _____	PARTICIPANT ID _____	VISIT TYPE _____	VISIT DATE (MM/DD/YYYY) ____/____/____
---------------------------	-------------------------	---------------------	--

**Section A. Basic Cigarette Use Information**

1. Have you smoked at least 100 cigarettes (5 packs = 100 cigarettes) in your entire life?

- Yes
- No → **Skip to Section B**
- Don't know/Not sure → **Skip to Section B**

2. How old were you when you first smoked a cigarette (even one or two puffs)?

\_\_\_\_\_ Years old

3. How old were you when you first began smoking cigarettes regularly?

\_\_\_\_\_ Years old

Check here if you have never smoked cigarettes regularly.

4. How many total years have you smoked (or did you smoke) cigarettes? Do not count any time you may have stayed off cigarettes.

\_\_\_\_\_ Years (If you smoked less than one year, write "1.")

5. On average when you have smoked, about how many cigarettes do you (or did you) smoke a day? (A pack usually has 20 cigarettes in it).

\_\_\_\_\_ Number of cigarettes per day

6. Do you NOW smoke cigarettes?

- Everyday
- Some days
- Not at all → **Skip to question 8**

7. How soon after you wake up do you smoke your first cigarette?

- Within 30 minutes
- After 30 minutes

8. How long has it been since you last smoked a cigarette (even one or two puffs)?

*First check which one of the following choices applies to you. Then, if applicable, write a number on the line for how many days, weeks, months, or years it has been since your last cigarette.*

- I smoked a cigarette today (at least one puff)
- 1-7 days → Number of days since last cigarette \_\_\_\_\_
- Less than 1 month → Number of weeks since last cigarette \_\_\_\_\_
- Less than 1 year → Number of months since last cigarette \_\_\_\_\_
- More than 1 year → Number of years since last cigarette \_\_\_\_\_
- Don't know/Don't remember

**Section B. Use of Other Forms of Tobacco**

9. Have you ever used other forms of tobacco, not including cigarettes?

- Yes
- No → **Skip to Section C**

10. How often do you/did you use other forms of tobacco?

- Every day → Number of times per day \_\_\_\_\_
- Some days → Number of days \_\_\_\_\_ per  Week  Month  Year

11. Which of the following products have you ever used regularly?

***Check all that apply***

- Cigarettes
- E-cigarettes or other electronic nicotine delivery system
- Traditional cigars, cigarillos or filtered cigars
- Pipes
- Hookah
- Clove cigarettes or kreteks
- Bidis
- Smokeless tobacco, like dip, chew, or snuff
- Snus
- Paan with tobacco, gutka, zarda, khaini
- Other, Please specify: \_\_\_\_\_

12. If you do not currently use other forms of tobacco, but did in the past, how long has it been since you last used other forms of tobacco regularly?

- Within the past month (0 to 1 month ago)
- Between 1 and 3 months (1 to 3 months ago)
- Between 3 and 6 months (3 to 6 months ago)
- Between 6 and 12 months (6 to 12 months ago)
- Between 1 and 5 years (1 to 5 years ago)
- Between 5 and 15 years (5 to 15 years ago)
- More than 15 years ago
- Don't know/Not sure
- Never used other forms of tobacco regularly

**Section C. Second-Hand Smoke Exposure**

13. Are you currently living with a smoker?

- Yes
- No

14. In the past 30 days, have you lived in a place where other people smoked cigarettes indoors?

- Yes
- No

15. In the past 30 days, have you worked in a place where other people smoked cigarettes indoors?

- Yes
- No

16. Thinking of all your childhood and adult years, have you ever lived in a place where other people smoked cigarettes indoors?

- Yes    In total, for about how many years? \_\_\_\_\_ If less than 1, write "1."
- No

17. Thinking of all the years you have worked, have you ever worked in a place where other people smoked cigarettes indoors?

- Yes    → In total, for about how many years? \_\_\_\_\_ If less than 1, write "1."
- No

Signature of Individual Completing This Form \_\_\_\_\_ Date \_\_\_\_/\_\_\_\_/\_\_\_\_\_  
(MM/DD/YYYY)

Name of Individual Completing This Form (please print) \_\_\_\_\_

**APPENDIX G**

**Alcohol and Tobacco Use Assessment Questionnaires – Month 12**

# Proprietary of MD Anderson Cancer Center

MDA2016-07-02  
Protocol Version 20, Dated 02/07/2022

## ALCOHOL ASSESSMENT – MONTH 12

INSTITUTION CODE	PARTICIPANT ID	VISIT TYPE	VISIT DATE (MM/DD/YYYY)
_____	_____	_____	____/____/____

### Instructions:

**For the following questions about drinking alcoholic beverages, a drink means a 12 oz. beer, a 5 oz. glass of wine, or one and a half ounces of liquor.**

1. During the past 30 days, did you drink any alcoholic beverages?

- Yes
- No **(End)**
- Refused **(End)**
- Don't know/Not sure

2. During the past 30 days, how many days per week or per month did you drink any alcoholic beverages, on the average?

\_\_\_\_\_ (Enter number of days you drank based on the timeframe checked below. Enter 0 if you did not drink.)

- Week
- Month
- Refused
- Don't know/Not sure

3. On the days when you drank, on average, about how many drinks did you have?

\_\_\_\_\_ (Enter the average number of drinks you had per day.)

- Refused
- Don't know/Not sure

4. In the past 30 days, on how many days did you have 5 or more drinks per day?

\_\_\_\_\_ Number of times

- None
- Do not know/Not sure

Signature of Individual Completing This Form \_\_\_\_\_ Date \_\_\_\_/\_\_\_\_/\_\_\_\_  
(MM/DD/YYYY)

Name of Individual Completing This Form (please print) \_\_\_\_\_

**TOBACCO ASSESSMENT – MONTH 12**

INSTITUTION CODE _____	PARTICIPANT ID _____	VISIT TYPE _____	VISIT DATE (MM/DD/YYYY) ____/____/_____
---------------------------	-------------------------	---------------------	---

1. Do you NOW smoke cigarettes?

- Everyday
- Some days
- Not at all → **Skip to Question 3**
- Never Smoked → **Skip to Question 4.**

2. On average, when you smoked, about how many cigarettes do you (or did you) smoke a day? (A pack usually has 20 cigarettes in it).

\_\_\_\_\_ Number of cigarettes per day

3. How long has it been since you last smoked a cigarette (even one or two puffs)?

*First check which one of the following choices applies to you. Then, if applicable, write a number on the line for how many days, weeks, months, or years it has been since your last cigarette.*

- I smoked a cigarette today (at least one puff)
- 1-7 days → Number of days since last cigarette \_\_\_\_\_
- Less than 1 month → Number of weeks since last cigarette \_\_\_\_\_
- Less than 1 year → Number of months since last cigarette \_\_\_\_\_
- More than 1 year → Number of years since last cigarette \_\_\_\_\_
- Don't know/Don't remember

4. Since your last visit, have you used other forms of tobacco, not including cigarettes?

- Yes
- No (**End**)

5. How often do you/did you use other forms of tobacco?

- Every day → Number of times per day \_\_\_\_\_
- Some days → Number of days \_\_\_\_\_ per  Week  Month  Year

6. Since your last visit, which of the following products have you used? ***Check all that apply***

- Cigarettes
- E-cigarettes or other electronic nicotine delivery system
- Traditional cigars, cigarillos or filtered cigars
- Pipes
- Waterpipe
- Hookah
- Clove cigarettes or kreteks
- Bidis
- Smokeless tobacco, like dip, chew, or snuff
- Snus
- Paan with tobacco, gutka, zarda, khaini
- Other, Specify \_\_\_\_\_

7. If you do not currently use other forms of tobacco, but did in the past, how long has it been since you last used other forms of tobacco regularly?

- Within the past month (0 to 1 month ago)
- Between 1 and 3 months (1 to 3 months ago)
- Between 3 and 6 months (3 to 6 months ago)
- Between 6 and 12 months (6 to 12 months ago)
- Between 1 and 5 years (1 to 5 years ago)
- Between 5 and 15 years (5 to 15 years ago)
- More than 15 years ago
- Don't know/Not sure
- Never used other forms of tobacco regularly

The following instructions pertain to questions 8 - 10. During each of the following time frames, please indicate whether you smoked cigarettes every day, some days, or not at all.

8. During study treatment

- Smoked every day
- Smoked some days
- Did not smoke at all
- Don't know/not sure
- Not applicable

9. After the end of study treatment

- Smoked every day
- Smoked some days
- Did not smoke at all
- Don't know/not sure
- Not applicable (I have not completed the study treatment)

10. Since your last visit to this clinic

- Smoked every day
- Smoked some days
- Did not smoke at all
- Don't know/not sure

Signature of Individual Completing This Form \_\_\_\_\_ Date \_\_\_ / \_\_\_ / \_\_\_\_\_  
(MM/DD/YYYY)

Name of Individual Completing This Form (please print) \_\_\_\_\_

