#### ***Rationale for including Alcohol and Tobacco Assessment Questionnaires***

Increasing evidence suggests that tobacco and alcohol use are risk factors in the development of intraepithelial neoplasia and cancer. In addition, tobacco and alcohol use may adversely affect agent intervention, for example by altering the safety profile or metabolism of a drug. Standardized assessments of tobacco and alcohol use during clinical trials will aid in understanding the potential relationship between the use of these products and clinical endpoints or cancer prevention biomarkers. Therefore, NCI, DCP is including assessment of tobacco and alcohol use at baseline and Month 12 to determine the potential impact

of tobacco and alcohol use on 1) treatment toxicity and symptom burden, and 2) the efficacy of treatment intervention.

In summary, the overall objective is to evaluate whether daily application of 4 mg of 4-OHT topical gel (2 mg per breast) versus placebo lowers breast density in women with mammographically dense breast.

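### On the Month 12 tobacco form, a No at Question 4 ends the form, so women who used no tobacco other than cigarettes never reach the items on smoking during treatment

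*Combined protocol and SAP*

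**What the plan says.** Section 2.3 (rationale for the alcohol and tobacco questionnaires) gives the purpose, which is to learn the effect "of tobacco and alcohol use on 1) treatment toxicity and symptom burden, and 2) the efficacy of treatment intervention". Tobacco is assessed twice, at baseline (Appendix F) and at Month 12 (Appendix G). Under the COVID-19 plan the Month 13-18 visit uses the Month 12 form.

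The Month 12 form runs as follows.

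- Question 1: "Do you NOW smoke cigarettes". Question 2 is the number per day. Question 3 is the time since the last cigarette.
- Question 4: "Since your last visit, have you used other forms of tobacco, not including cigarettes". A No is marked as the end of the form.
- Questions 5 to 7 concern other tobacco.
- Questions 8 to 10 return to cigarettes. Their lead-in begins "The following instructions pertain to questions 8 - 10", and for each period it says "please indicate whether you smoked cigarettes every day, some days, or not at all". Question 8 is headed "During study treatment". Question 9 covers the time after treatment, and Question 10 the time since the last clinic visit.

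At the equivalent gate (Question 9), the baseline form moves the respondent on: "No → Skip to Section C".

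**The concern.** Access to three cigarette questions is decided by a question that excludes cigarettes. If the form is followed as printed, a woman who smokes only cigarettes is never asked how often she smoked while using the gel.

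Two features suggest a routing slip and not a choice. The baseline form sends the same answer onward. The response options in Questions 8 to 10 also include not having smoked at all and, for Question 9, not having finished treatment, which suit respondents in general and not just users of other tobacco.

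At stake is the purpose stated in Section 2.3: relating tobacco use to toxicity, symptoms and efficacy calls for exposure during treatment. A second risk lies in data handling, since a blank on these items carries no information about smoking and the documents give no rule for coding it.

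**Working it through.** The documents state no figure to reproduce here. The check is a trace of the printed skip instructions in Appendix G for each type of respondent.

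| Respondent | Path as printed | Reaches Questions 8-10? |
|---|---|---|
| Current cigarette smoker, no other tobacco since last visit | 1, 2, 3, 4 (No), end | No |
| Former smoker, including one who quit on gel, no other tobacco | 1, 3, 4 (No), end | No |
| Never-smoker, no other tobacco | 1, 4 (No), end | No |
| Any woman with other tobacco use since last visit | 1, (2), (3), 4 (Yes), 5-7, 8-10 | Yes |

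**Does another item cover the treatment period?**

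- Baseline Question 6 gives smoking status before treatment.
- Month 12 Question 1 gives status on the day of the visit.
- Month 12 Question 2 gives the daily number, but a woman who answers that she does not smoke now skips it.
- Month 12 Question 3 gives recency. Combined with gel dates, it largely shows whether a woman who quit had smoked on treatment. It is less clear near one year and for the longer Month 13-18 course.
- None of these asks how often she smoked over the treatment period. Only Question 8 does.

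**What the remaining items cannot separate.** Take two hypothetical women, both daily smokers at baseline, both using no other tobacco, and both with a last cigarette six months before the Month 12 visit. One smoked daily until she quit; the other cut down to some days soon after starting gel. Baseline Question 6 and Month 12 Questions 1 and 3 are identical for both, and Question 2 is skipped by both. Question 8 is the item that could tell them apart.

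Now take a woman who stops gel early and completes the form at Month 12. Section 8.4 keeps such women on study where possible. Questions 1 to 3 describe her smoking at a visit long after gel ended. Only Questions 8 and 9 together ask about the two periods separately.

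**With the routing changed.** If No at Question 4 led to Question 8, every row of the table would reach Questions 8 to 10.

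**The case against.** The case for leaving the form alone has real content.

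- *Much smoking information survives.* The form is completed at the visit that closes treatment. A cigarette-only smoker has already given frequency now, number per day and recency before Question 4. This stands. A reader might infer that such women have no record of smoking on treatment at all, and the documents do not support that.
- *A comparison group exists.* On Question 8 alone, every woman who reports not smoking would be a user of another product, so a reader might infer that no tobacco-free reference group is available. That does not follow: never having smoked at Question 1, with No at Question 4, identifies never-smokers with no recent other tobacco use, and all women reach both items.
- *No one has said that blanks will be coded as non-smoking.* Correct. Answers to Questions 1 to 3 would contradict that coding for any current or recent smoker. The coding rule is a precaution, not a response to a stated error.
- *No count can be supported.* The number of smokers without Question 8 is N × (share who smoke) × (share of those using no other tobacco). The documents give neither share. Purely assumed values of 5-15% and 70-90%, with N from the 128 expected evaluable to the 158 randomized (Section 13.1), give 128 × 0.05 × 0.70 = 4.5 up to 158 × 0.15 × 0.90 = 21.3. That range reflects only the assumptions, and these women would lack only the Question 8-10 detail.
- *No analysis depends on it.* Tobacco is in none of the objectives in Sections 1.1 to 1.3, and Section 13 names no tobacco covariate, subgroup or model. This stands and limits the importance of the point.
- *The end instruction might mean only the end of the other-tobacco block.* Nothing on the form says so, and the Month 12 alcohol form uses the same marker to stop. If sites read it differently, the data would be inconsistent, which is also a reason to correct it.

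**Conclusion.** The routing fault is certain on the printed form, and its reach is narrow. Women who used no other tobacco since the last visit, including cigarette-only smokers and women who quit on gel, are never asked Questions 8 to 10. Whatever detail on treatment-period frequency and on-gel versus off-gel smoking cannot be reconstructed from the other items is lost. The number of women this concerns cannot be computed from the documents.

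The effect is confined to the tobacco-impact assessment described in Section 2.3. The primary comparison and the listed secondary and exploratory objectives are untouched. The conclusion assumes that sites follow the skip instruction as printed. It is a minor correction worth making because it is cheap and serves a purpose the protocol itself states.

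**What to change.** 1. In Appendix G, Month 12 tobacco form, change the No option at Question 4 from ending the form to skipping to Question 8, matching the onward skip at the baseline gate.
2. For forms already completed, record in the data-handling rules that blank Questions 8 to 10 after No at Question 4 are missing by design and are never to be read as not having smoked. Derive what can be derived from baseline Question 6 and Month 12 Questions 1 and 3, together with gel start and stop dates.
3. Optional: let never-smokers leave after the other-tobacco items, and route women who smoked at any time since starting gel through Question 2 even if they do not smoke now. Neither is needed to cure the fault.

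The cost is a CRF amendment, which Section 12.2 sends to the DCP Protocol Information Office for approval before deployment, and up to three more tick-box items per woman. No visit or procedure is added. Because Section 2.3 describes the assessments as standardized, the amendment should note the changed skip so that any comparison with data from the unchanged form allows for it. The new skip cannot recover answers on forms already completed, so the coding rule is needed in any case.
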